114 intervention and at 6- and 12-month follow-up.

115 The primary hypothesis that will be tested is that the program will be feasible and effective in
116 increasing the psychological functioning of the person.

117 The secondary hypothesis will test whether participants assigned to the experimental condition will
118 show a reduced level of stress, anxiety, depression, and fear of COVID-19, as well as improved
119 emotion regulation strategies, self-efficacy, and psychological well-being than those in the WL
120 condition at treatment termination.

121 Moreover, participants in the experimental condition will be expected to present maintained outcomes
122 or further decreased psychological symptoms at 6 and 12-month after the end of the treatment
123 program.

124 **METHODS**

125 **Design**

126 The project consists of a prospective, randomized, open, and parallel group-controlled study with two
127 arms: an experimental arm with 8 online weekly CBT self-help sessions, and a waiting list (WL)
128 control arm.

129 **Ethical Statement**

130 The study was approved by the Ethical Committee of the Catholic University of Milan, Italy (ID: 25-
131 21). All procedures performed in the study will be run following the ethical standards of the
132 institutional and/or national research committee and with the Helsinki Declaration and its later
133 amendments or comparable ethical standards.

134 **Patients and public involvement**

135 Participants from the general population will be recruited through advertisements placed on social
136 media platforms (i.e., Facebook, Instagram, Twitter), and online webinars on the topic.
137 The recruitment materials will include details about the study aim, the treatment delivered, and the
138 conditions for participation, together with the weblink to access the program.

139 Inclusion criteria for the participants into the study will be: (A) being fluent in the Italian language;
140 (B) being over 18 years old; (C) providing online informed consent; and (D) showing
141 mild/subthreshold levels of symptoms at the 12-Item General Health Questionnaire (GHQ-12) -
142 Italian version (50, 51) - the most extensively used screening tool assessing the severity of common
143 mental disorders over the past few weeks using a 4-point Likert-type scale (from 0 to 3). Its total
144 score ranges from 0 to 36, with high scores indicating worse health status. Only participants who

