145 score ≥ 15 on the GHQ and show moderate levels of symptoms at the clinical interview will be
146 included in the study.

147 Participants will be excluded from the program if: (A) presenting visual, hearing, or cognitive
148 impairments that will prevent them from receiving and following the intervention; (B) suffering from
149 severe psychiatric disorders according to the Diagnostic and Statistical Manual of Mental Disorders
150 (DSM 5) (52); (C) lacking basic computer skills or internet access.

151 Respondents will not be excluded if already receiving psychopharmacological therapy or
152 psychological-psychotherapeutic support.

153 **Sample size calculation**

154 The minimum sample size required to conduct this study was calculated using an a priori sample size
155 calculator (G*Power 3.1.9.2 software) for *F* tests (53-55). Participants were randomly divided into
156 two groups: (A) iCBT self-help and (B) waiting list control. Moreover, participants will be measured
157 in 3 moments: (1) before the intervention, (2) at the end of intervention (two months later), and (3)
158 after 12 months from treatment termination. Due to the novelty of the study from which to derive
159 realistic estimates of effect sizes, the partial η^2 was set a priori to assume a value of 0.02 – small
160 effect size (56, 57) – which provides a Cohen's *f* value of 0.143. Moreover, the type I error (α) rate
161 was set at 0.05 (two-sided) and the Power ($1 - \beta$) was set at 0.95, and the a priori correlation between
162 repeated measures was set at 0.50, according to general guidelines (56). Lastly, the non-sphericity
163 correction was set to 1. Results showed that there is a 95% chance of correctly rejecting the null
164 hypothesis of no significant effect of the interaction with 128 participants in total (64 for each group).

165 **Randomization and blinding**

166 The random randomization scheme will be generated using the Web site Randomization.com (58).
167 Allocation concealment will be ensured by the program generating an anonymous code for each
168 participant that will be associated with the randomization sequence. Due to the nature of the
169 intervention, the treatment group allocation cannot be concealed from the participants, nor the
170 research team and assessor of outcomes. Participants will be assigned to one of two conditions within
171 2 working days from their baseline assessment (Figure 1).

172

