173 *** PLEASE INSERT Figure 1: Flow chart of the RinasciMENTE study

174 **Measures**

175 *Demographic and clinical information.* Information about age, gender, education, civil status, weight, and
176 high - used to calculate the Body Mass Index (BMI, kg/m²) in presence of dysfunctional eating behaviors
177 - will be self-reported online at baseline. Subjects will be also asked to provide information about the
178 country where they are currently living, their work situation (before and after the COVID-19 pandemic),
179 and the personal experience they made of both COVID-19 pandemic and related preventive measures.
180 The Italian version of the following psychological measures will be also collected at baseline (T0),
181 treatment termination after 2 months (T1), at 6-month (T2), and 12-month (T3) follow-up in the
182 experimental condition only). Please see Figure 2 for a detailed project timeline.

183 *** INSERT GANTT Figure 2: Gant of the RinasciMENTE study

184 Primary outcome:

185 *Outcome Questionnaire (OQ-45)* (59) composed by 45 items rated on a 5-point Likert scale (0 = Never –
186 4 = Almost always) assessing the treatment progresses across 3 different domains: Symptom Distress (SD
187 – 25 items: 2, 3, 5, 6, 8, 9, 10, 11, 13, 15, 22, 23, 24, 25, 27, 29, 31, 33, 34, 35, 36, 40, 41, 42 and 45),
188 Interpersonal Relations (IR – 11 items: 1, 7, 16, 17, 18, 19, 20, 26, 30, 37 and 43), and Social Role (SR –
189 9 items: 4, 12, 14, 21, 28, 32, 38, 39 and 44). The OQ-45 total score is calculated by summing the score of
190 the three subscales. Total score (range 0 to 180) is calculated by the sum of the items.

191 *Secondary outcomes:*

192 *Perceived stress scale* (PSS) (60), composed of 10 items rated on a 5-point Likert scale (from 0 = never to
193 4 = very often) assessing the degree to which situations in one's life are appraised as stressful. PSS scores
194 are obtained by reversing responses (i.e., 0 = 4, 1 = 3, 2 = 2, 3 = 1 and 4 = 0) to the four positively stated
195 items (items 4, 5, 7, and 8) and then summing across all scale items. The total score (range 0 to 40) is
196 calculated by the sum of the items.

197 *Emotional regulation questionnaire (ERQ)* (61), composed of 10 items rated on a 7-point Likert scale
198 (from 1 = strongly disagree to 7 = strongly agree) assessing respondents' tendency to regulate their

199 emotions in two ways: Cognitive Reappraisal (items 1, 3, 5, 7, 8, and 10) and Expressive Suppression

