200 (items 2, 4, 6, and 9). The total score (range 7 to 70) is calculated by the sum of the items.

201 *Depression Anxiety Stress Scales-Short Version* (DASS-21) (62), composed by 21 statements rated on a
202 4-point Likert scale (from 0 = did not apply to me at all to 3 = applied to me very much) assessing the
203 negative emotional states of depression, anxiety, and stress. Each of the three DASS-21 scales contains 7
204 items: *Depression*: dysphoria, hopelessness, devaluation of life, self-deprecation, lack of
205 interest/involvement, anhedonia, and inertia - (Items 3, 5, 10, 13, 16, 17, and 21); *Anxiety*: autonomic
206 arousal, skeletal muscle effects, situational anxiety, and subjective experience of anxious affect -
207 (Items 2, 4, 7, 9, 15, 19, and 20); *Stress*: levels of chronic nonspecific arousal, difficulty relaxing,
208 nervous arousal, and being easily upset/agitated, irritable/over-reactive and impatient - (Items 1, 6, 8,
209 11, 12, 14, and 18). Sum scores are computed by adding up the scores on the items per (sub)scale and
210 multiplying them by 2. Sum scores for the total DASS-total scale thus range between 0 and 126, and
211 those for each of the subscales may range between 0 and 42. Ranges of scores correspond to levels
212 of symptoms, ranging from “normal” to “extremely serious”. Notably, the DASS-21 has been recently
213 used to investigate the impact of the COVID-19 pandemic on the physical and mental health of
214 different populations worldwide (63-65).

215 *Fear of COVID-19 Scale* (FCV-19S) (66) composed by 7-item rated on a 5-point scale, ranging from 1
216 (from 1 = strongly disagree to 5 = strongly agree) reflecting cognitive, emotional, behavioral, and
217 physiological manifestations of fear related to COVID-19. The total score (range 7 to 35) is calculated by
218 the sum of the items. All items are positively worded, implying that higher scores indicate greater levels of
219 fear.

220 *General Self-efficacy Scale* (GSES) (67), composed of 10 items rated on a 4-point Likert scale (from
221 1 = Not at all true to 4 = exactly true) assessing the individuals’ confidence in their ability to cope
222 with a variety of difficult or stressing situations. The total score is calculated by finding the sum of

223 all items. For the GSE, the total score ranges between 10 and 40, with a higher score indicating more
224 self-efficacy.

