281 communicating the update of the new material on the platform. Participants who will not access the
282 material or that will not complete the suggested tasks and exercises will receive a weekly reminder
283 containing a brief encouraging message every Monday.

284 At the end of the program (after two months – T1), participants in both conditions will be asked to
285 fill in the baseline questionnaires again. Then, the experimental group will be also assessed after 6-
286 and 12 months from the term of the treatment (T2 and T3) (Figure 1).

287 **Statistical analysis**

288 Statistical analyses were performed using SPSS software ver. 24.0 (76).

289 First, preliminary analyses will be performed to test the assumptions of both univariate and
290 multivariate normality: if (strong) violations will be detected, robust methods or data transformation
291 will be applied. Dropouts will be excluded from the study.

292 A missing values analysis will be run to see if the values are Missing Completely at Random
293 (MCAR), or if there is some pattern among missing data. If there are no patterns detected, then
294 pairwise or listwise deletion will be done to deal with missing data. However, if the missing values
295 analysis detects a pattern, then imputation will be done.

296

297 The demographic characteristics will be reported as means and standard deviations for continuous
298 variables, and frequencies and percentages for categorical variables.

299 The chi-square statistic will be used to test the association between treatment groups and socio-
300 demographic and variables (i.e., age, gender, education, civil status, job), and correlation analysis
301 will be used to test the association between quantitative variables.
302 The outcomes will be compared in the two treatment conditions using an Intention-To-Treat (ITT)
303 approach. The significance level will be set at 5%.
304 A repeated-measures ANOVA will be used to determine whether there are any between and within
305 groups differences in the selected outcomes from baseline to treatment termination. , Then repeated-
306 measures within group ANOVA will test outcome differences over time baseline, end of treatment,
307 6- and 12-month follow-up) in the experimental group only (. Corrected effect sizes (Cohen's *d*) and
308 significance at 95% confidence interval (95% CI) will be calculated for both between-group and

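### After T1 there is no comparator, so a change in the pandemic over about 14 months can be reported as lasting or further programme benefit, or as relapse

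*Combined protocol and SAP*

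**What the plan says.** **Schedule.** Under Measures and Procedure, the psychological scales are completed at T0 and T1 in both arms. They are completed again 6 and 12 months after the end of treatment (T2, T3) in the experimental arm only. Procedure also opens the programme to the waiting list once the experimental arm has finished, at two months.

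**Analysis.** Statistical analysis plans a between- and within-group repeated-measures ANOVA from baseline to treatment termination. For the longer term it says "measures within group ANOVA will test outcome differences over time baseline, end of treatment", adds the two follow-up visits, and confines this test to the experimental group. It names no covariate or calendar term and exempts no outcome.

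**Expected result.** The hypotheses at the end of Background expect the experimental arm to hold its gains "or further decreased psychological symptoms at 6 and 12-month after the end of the treatment" programme.

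**The outcome closest to the pandemic.** The FCV-19S is a secondary outcome covering "physiological manifestations of fear related to COVID-19. The total score (range 7 to 35) is calculated by" summing its items.

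**Exposure items.** The demographic block "will be self-reported online at baseline. Subjects will be also asked to provide information about the" country of residence, work situation "and the personal experience they made of both COVID-19 pandemic and related preventive measures". No later collection of these items is stated.

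**Acknowledged limit.** Expected results concedes that environmental confounders may escape control. It attributes this to online delivery and attaches no analysis or limit on interpretation.

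**The concern.** Up to T1 both arms live through the same calendar period, so a change in infections, restrictions or the economy affects both and cancels in the comparison. After T1 nothing cancels it. The T0–T3 test in one arm asks only whether the mean moved, and the plan links movement or stability to the programme.

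The horizon is long. Recruitment starts on 21/02/2022, so the earliest T3 is about 23/04/2023 (61 days of treatment plus 365 days, ignoring screening time). The Abstract itself expects the period of interest to extend beyond the pandemic, and Background attributes the distress under study to the pandemic, isolation and recession.

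The error can go either way. An easing pandemic could be read as sustained or growing benefit, or could hide a fading effect. A new wave could be read as relapse. At stake is the 6- and 12-month claim, not the between-arm result at treatment end.

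**Working it through.** **Step 1. The plan's own figure.** Inputs from Sample size calculation:
- alpha "was set at 0.05 (two-sided) and the Power" "was set at 0.95, and the a priori correlation between" repeated measures 0.50
- "the partial η^2 was set a priori to assume a value of 0.02", so f = √(0.02/0.98) = 0.143
- two groups, three measurement times, non-sphericity correction 1

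For a group-by-time interaction, λ = N·f²·m/(1−ρ) = 128 × 0.143² × 3/0.5 = 15.70, with df 2 and 252. Power is 0.951, so the stated 128 (64 per arm) reproduces. That calculation concerns a two-arm interaction whose third time is 12 months after treatment. The schedule has no control observation at that time, so this power does not carry over to the single-arm follow-up test.

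**Step 2. Assumptions for the illustration.** No programme effect; 64 in the experimental arm; correlation 0.50 as in the plan; sphericity. The external fall of d SD by T3 is linear over months 0, 2, 8 and 14. Its size is assumed: d = 0.2, 0.3 and 0.5.

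**Step 3. Four-visit within-arm F test.** The visit means are 0, −d/7, −4d/7 and −d, with average −3d/7. The squared deviations sum to (9 + 4 + 1 + 16)/49 × d² = (30/49)d².

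λ = 64 × (30/49)d²/0.5 = 78.37d², with df 3 and 189.

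**Step 4. T1–T3 paired contrast.** This is the comparison that an expectation of further decrease concerns. It carries 12/14 of the drift.

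Standardised difference = (12/14)d/√(2(1−0.50)) = 0.857d. Noncentrality = 0.857d × √64 = 6.857d, with 63 df, two-sided 5%.

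| External fall by T3 | λ of F | F significant | T1–T3 noncentrality | T1–T3 significant |
|---|---|---|---|---|
| 0.2 SD | 3.13 | 28% | 1.37 | 27% |
| 0.3 SD | 7.05 | 58% | 2.06 | 53% |
| 0.5 SD | 19.59 | 97% | 3.43 | 92% |

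The nominal rate is 5% throughout.

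**Step 5. Sensitivity of the F test.** With 45 retained (an assumed 30% loss: 64 × 0.7 = 44.8), the figures are 20%, 43% and 88%. With 64 participants and a correlation of 0.70, they are 45%, 82% and above 99%. A fall of only 0.1 SD (n = 64, correlation 0.50) gives 10%.

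**Step 6. The randomised contrast.** In 4,000 simulated trials with a common 0.3 SD fall in both arms, 64 per arm and no programme effect, the between-arm comparison of T0–T1 change rejected in 5.0%. The exposure is confined to the single-arm part.

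**The case against.** **No drift is documented.** This stands. The plan says what the FCV-19S reflects, not how it moves over time, so the percentages show vulnerability and are not a forecast. They apply equally to natural recovery, or to regression to the mean after selection on GHQ-12 of 15 or more. That widens the reason for caution.

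**With no programme effect there would usually be no T1 benefit to call maintained.** This is fair for the T0–T3 figures. The T1–T3 figures do not need it: they hold unchanged if the programme has a real effect that stays constant from T1 to T3, and a decrease would then be credited to it wrongly.

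**The main hypothesis is safe and the limitation is acknowledged.** The between-arm hypothesis is set at treatment termination and is untouched. The acknowledgement, however, is general, and it leaves the 6- and 12-month expectation unqualified.

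**A tempting stronger reading.** A reader might infer that the fault lies in recording pandemic exposure and work situation once, and that repeating these items would cure it. The documents do not support this. Baseline-only is the natural reading, but the exposure sentence names no time point. The questionnaires given at baseline are repeated at T1, and the detailed timeline is in a figure not available here. More important, the percentages above would be identical if the items were asked at every visit. A trend shared by everyone in a single arm cannot be adjusted away, and splitting at most 64 people by status after baseline is debatable in itself.

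**Conclusion.** The point holds for the follow-up after T1, and its cause is the missing comparator. As planned, the T0–T3 analysis cannot tell a lasting or growing programme effect from an external change over about 14 months, in either direction. The FCV-19S is the clearest case; the OQ-45 and the other scales share the problem.

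Under the assumed linear drifts of 0.2 to 0.5 SD, the four-visit test would be significant in 28% to 97% of trials with no programme effect, and the T1–T3 contrast in 27% to 92%. These figures rest on 64 participants, a correlation of 0.50 and a drift size that the documents do not give.

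Nothing here supports the inference that the randomised T0–T1 result is biased by the pandemic. The consequence is limited to the long-term claim, and the correction is cheap enough to make.

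**What to change.** In Statistical analysis, and in the matching hypothesis in Background:

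1. State that inference about programme effect rests on the randomised T0–T1 comparison.
2. Report FCV-19S values at T2 and T3 descriptively by calendar date, and do not count them toward the maintenance claim.
3. Report T2–T3 results on the OQ-45 and the other scales as uncontrolled within-arm change, not as maintained or further programme benefit.

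Optionally, repeat the items on country, work situation and pandemic experience at T1, T2 and T3, for description only. This would show whose circumstances changed but would not correct for a shared trend.

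The cost is a few sentences of text, one less formal long-term test and a more modest long-term claim. No further participants are needed. The optional items would lengthen the follow-up forms slightly.

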309 within-group differences, while for the total effect will be calculated the Cohen's *f*.

310 **DISCUSSION**

311 To help and mitigate the impact of the COVID-19 pandemic on selected psychological parameters,
312 the objective of this study is to evaluate the effectiveness of an Internet-based self-help intervention
313 based on CBT principles and techniques, in reducing the level of stress, anxiety, depression, and fear
314 of COVID-19, while increasing emotions self-regulation and perceived self-efficacy of Italians both
315 living in the country and abroad. .

316 The online modality was chosen due to the current multiple barriers for face-to-face psychological
317 interventions (i.e., mobility), and its largely acknowledged advantages, including greater flexibility
318 or the possibility to reach rural or low-income population (77), and Italians living outside the country
319 who look for psychological support in their language. Also, the self-help approach to therapy will be
320 employed to further improve access to treatments and empower users to strengthen their self-
321 management ability, while putting less strain on therapeutic resources (78) than conventional
322 treatments do.

323

324 **Expected results**

325 The results of this RCT will provide evidence for the feasibility and effectiveness of the
326 RinasciMENTE program in supporting the emotional well-being of the persons. Specifically, people
327 are expected to show reduced levels of stress, anxiety, depression, and fear of COVID-19, as well as
328 improved emotion regulation strategies, and self-efficacy. They are also expected to acquire the skills
329 necessary to deal with the psychological consequences of social isolation during and after the
330 COVID-19 outbreak.

331 Still, among the weaknesses of this study, it must be anticipated possible lack of internet access and
332 digital literacy skills of some people.

333 Non-digital natives (i.e., older people) might, indeed, experience difficulties in the use of digital tools,
334 and social isolation can pose additional challenges to their usage (i.e., chaotic home environments,
335 limited privacy, or unreliable internet connection) (79).

336 The use of online intervention might also prevent effective controlling of confounding variables (i.e.
337 environmental factors) that might impact treatment outcomes (80).

338 The results from this study will help to detect and address any usability problem, as Internet-based

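### The only ERQ score the plan defines is an undirected sum of two different strategies, so it cannot show which strategy changed or whether emotion regulation improved

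*Combined protocol and SAP*

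**What the plan says.** In Methods, Measures (secondary outcomes), the ERQ is "composed of 10 items rated on a 7-point Likert scale", with anchors "from 1 = strongly disagree to 7 = strongly agree". It is said to assess how respondents regulate their "emotions in two ways: Cognitive Reappraisal (items 1, 3, 5, 7, 8, and 10) and Expressive Suppression", and the entry then closes with the suppression items and the scoring rule: "items 2, 4, 6, and 9). The total score (range 7 to 70) is calculated by the sum of the items".

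The ERQ serves the secondary hypothesis in the Background. Participants in the experimental arm are to "show a reduced level of stress, anxiety, depression, and fear of COVID-19, as well as improved" "emotion regulation strategies, self-efficacy, and psychological well-being than those in the WL" condition at the end of treatment. The Expected results section repeats the prediction: "improved emotion regulation strategies, and self-efficacy. They are also expected to acquire the skills".

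The Statistical analysis section plans a repeated-measures ANOVA on the selected outcomes at a 5% level. It names no ERQ subscale and does not say which ERQ score enters the model.

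**The concern.** The hypothesis is about strategies, and the plan itself separates two of them. A sum over both is interpretable as improvement only if the plan says which way each strategy should move and the items are scored to match. It does neither. A rise in the total could come from more reappraisal, more suppression or both, and the three would look alike. A participant who swaps one strategy for the other could show no change.

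The risk is that a named secondary hypothesis has no decision rule. The choice among total, reappraisal and suppression would then be made with the data in hand, in an open trial where participants, research team and outcome assessors all know the allocation.

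The stated range also conflicts with the item count and anchors given in the same entry.

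**Working it through.** **1. The stated range.** Inputs from the ERQ entry: 10 items, anchors 1 to 7, split 6 and 4. The range of a plain sum runs from items × lowest anchor to items × highest anchor.

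- Total: 10 × 1 = 10 to 10 × 7 = 70. The stated 7 to 70 is not reproduced. Totals of 7, 8 and 9 cannot occur; the upper bound is right.
- Alternatives do not give 7 to 70 either. Seven items anchored 1-7 give 7-49, and ten items anchored 0-7 give 0-70. Reversing the suppression items (8 − x) leaves 10-70.
- Cognitive Reappraisal: 6 × 1 = 6 to 6 × 7 = 42.
- Expressive Suppression: 4 × 1 = 4 to 4 × 7 = 28.

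**2. How neighbouring scales are specified.** The PSS entry says which items are reversed. The DASS-21 entry defines sums and ranges per subscale. The FCV-19S and GSES entries say what a higher score means, and the GSES, also ten items anchored at 1, has the correct minimum of 10. The ERQ entry has no reversal, no subscale score and no direction.

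**3. What the sum can show.** Change in total = change in reappraisal + change in suppression.

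- Reappraisal +3, suppression 0: total +3.
- Reappraisal 0, suppression +3: total +3, the same result from a different strategy.
- Reappraisal +3, suppression −3: total 0.
- Reappraisal +3, suppression −2: total +1.

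**4. Illustration of the loss of power.** The documents give no ERQ SDs and no expected ERQ changes, so these are assumptions. With two time points the group-by-time test is equivalent to a two-sample t-test on change scores. The SDs below therefore stand for SDs of change in reappraisal/suppression, and the shifts for differences between arms. Changes in the two subscales are taken as uncorrelated. There are 64 per arm (Sample size calculation section), with none lost, and a two-sided 5% test.

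Formulas: SD of total = √(SD_R² + SD_S²); d = shift / SD; noncentrality = d × √(64/2); power from the noncentral t with 126 degrees of freedom.

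For SDs 7/5, SD of total = √(49 + 25) = 8.60. With +3 and −2, the total has d = 1/8.60 = 0.12. With +3 alone it has d = 3/8.60 = 0.35.

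| Assumed SDs | Reappraisal ±3: d, power | Suppression ±2: d, power | Total, +3 and −2: d, power | Total, +3 only: d, power |
|---|---|---|---|---|
| 6/4 | 0.50, 0.80 | 0.50, 0.80 | 0.14, 0.12 | 0.42, 0.65 |
| 7/5 | 0.43, 0.67 | 0.40, 0.61 | 0.12, 0.10 | 0.35, 0.50 |
| 8/6 | 0.38, 0.56 | 0.33, 0.46 | 0.10, 0.09 | 0.30, 0.39 |

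The opposite-shift column is close to the worst case, because the two changes nearly offset. When only reappraisal moves, the total loses power because the suppression items add variance without signal, but it does not collapse.

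**The case against.** The best defence is that the plan is ambiguous rather than committed to the sum. The Statistical analysis section never says the ERQ total is the analysed variable, the subscale items are listed, and the hypothesis speaks of strategies in the plural. The OQ-45 entry has the same form, with subscales listed and then a total. All items are collected, so both subscales can be computed at any time. This stands in part: the documents do not prove that the sum alone will be tested. But the total is the only ERQ score defined anywhere, and leaving the choice until the data are seen is what prespecification should prevent.

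A second defence is that offsetting requires reappraisal to rise while suppression falls. The documents never predict this, and never say that less suppression is a benefit. This stands in full. A reader might infer that the total will hide a real effect; the documents support only the conditional statement. The missing direction is a defect whichever way the strategies move.

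A reader might also infer that any rise in the total would be reported as improvement. The plan does not say so, since it gives no direction for the ERQ at all.

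Finally, the range slip might be taken as a scoring fault. Only the printed lower bound is wrong; no item, score or test changes because of it.

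**Conclusion.** The point holds as a gap in a secondary outcome that should be closed. As defined, the ERQ total cannot identify which strategy changed and has no direction by which to judge improvement, so it does not answer the hypothesis it serves. This follows from the plan's own text and needs no outside source.

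The size of any power loss depends on assumptions the documents do not supply. Over the assumed SDs, the total's power is about 0.09 to 0.12 if the strategies move in opposite directions as illustrated, and about 0.39 to 0.65 if only reappraisal moves. These figures show how the result depends on the pattern of change; they do not forecast the trial. The range of 7 to 70 is a minor error, correctly 10 to 70. The primary OQ-45 analysis and the sample size of 128 are not affected.

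**What to change.** In the Measures section, replace the ERQ total with two separately prespecified secondary outcomes: Cognitive Reappraisal (items already listed, range 6-42) and Expressive Suppression (items already listed, range 4-28). State the expected direction of each. In the Statistical analysis section, name these two scores as the ERQ variables to be analysed. Delete the total, or keep it labelled as descriptive with its range corrected to 10-70.

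The cost is a wording change and one additional secondary test (two scores in place of one). No new data are needed.
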